### 6.5 Guidelines for the Management of Dry Skin and Skin Toxicity

Guidelines for the management of dry skin are provided below.

#### General prophylaxis:

- Avoid unnecessary exposure to sunlight and excessive use of soap.
- Avoid bathing in excess; use tepid rather than hot water.
- Use moisturizers regularly; apply thick, alcohol-free and oil-in-water based emollient cream on exposed and dry areas of the body.
- Avoid perfumed products, bubble bath, perfumed soaps, and take breaks from shaving.
- Use broad spectrum sunscreen with a skin protection factor (SPF)  $\geq 15$ .
- Wear cotton clothes next to skin rather than wool, synthetic fibers, or rough clothing.
- Use occlusive alcohol-free emollient creams (jar or tub) for treatment of mild/moderate xerosis.
- For scaly areas, use exfoliants (ammonium lactate 12% or lactic acid cream 12%).

#### Guidelines for Management of Dry Skin

Grade and Definition	Study Drug Management	Medical Management
Grade 1: Dry skin covering less than 10% body surface area (BSA) and no associated erythema or pruritus	Continue study drug at current dose.	Use fragrance free moisturizing cream or ointment BID over entire body. Use ammonium lactate 12% cream or salicylic acid 6% cream BID over dry/scaly/hyperkeratotic areas such as palms and soles.
Grade 2: Dry skin covering 10 to 30% BSA and associated with erythema or pruritis with limited instrumental activities of daily living (IADL)	Continue study drug at current dose.	Use fragrance free moisturizing cream or ointment BID over entire body. Use ammonium lactate 12% cream or salicylic acid 6% cream BID over dry/scaly/hyperkeratotic areas such as palms and soles. Use zinc oxide 13-40% at night for areas with fissures.
Grade 3: Dry skin covering $>30\%$ BSA and associated with pruritis; limiting self-care activities of daily living (ADL)	Hold study drug (for up to 14 days), with weekly reassessments of clinical condition. When resolves to $\leq$ Grade 1 or baseline, restart at 1 dose level below in consultation with the Study Chair.	Use topical steroid ointment or cream* BID and zinc oxide 13-40% at night for areas with fissures.
Grade 4: Dry skin with life-threatening consequences, urgent intervention indicated	Discontinue study drug.	Evaluation and therapy as clinically indicated

\*Topical Steroid Ointments: Clobetasol 0.05%, Betamethasone 0.05%, Fluocinonide 0.05%

## 6.6 Dose Modifications for Dermatology/Skin Disorders

Grade	Action
Grade 1 or 2	
 
Maintain dose
 

Intolerable Grade 2; Grade 3	
 
Hold erdafitinib until resolution to <math>\leq</math> tolerable Grade 2 and dose reduce as per Section 6.2.
 

## 6.7 Guidelines for Management of Nail Toxicity (Onycholysis, Onychodystrophy, and Paronychia)

### General Prophylaxis:

- Good hygienic practices, keep fingers and toes clean.
- Keep nails trimmed
- Use gloves for housecleaning and gardening to minimize damage and prevent infection
- Nail polish and imitation fingernails should not be worn until the nails have grown out and returned to normal
- Wearing comfortable shoes (wide sized shoes with room for the toes)
- Trimming nails but avoiding aggressive manicuring

### Guidelines for Management of Nail Discoloration/Loss/Ridging (Onycholysis/Onychodystrophy)

Grade and Definition	Study Drug Management	Medical Management
Grade 1: Asymptomatic; clinical or diagnostic observations only, intervention not indicated	Continue study drug at current dose,	Over the counter nail strengthener OR poly-urea urethane nail lacquer (Nuvail) OR diethylene glycol monoethylether nail lacquer daily (Genadur)
Grade 2: Symptomatic separation of the nail bed from the nail plate or nail loss, limiting instrumental ADLs	Continue study drug at current dose. Consider holding study drug if no improvement in 1 to 2 weeks. When resolves to $\leq$ Grade 1 or baseline, restart at same or at a reduced dose ( Appendix IV ) in consultation with the Study Chair.	For signs of infection (periungal edema/erythema/ tenderness and/or discharge), obtain bacterial cultures, and then start the following: 
 
treatment with oral antibiotic for 2 weeks (cefadroxil 15 mg/kg/dose (up to 500 mg/dose) every 12 hours, ciprofloxacin 15 mg/kg/dose (up to 500 mg/dose) every 12 hours, or sulfamethoxazole/trimethoprim (TMP) 6 to 12 mg TMP/kg/day in divided doses every 12 hours; maximum single dose: 160 mg TMP/dose)
 
 AND 
 
topical antifungal lacquer daily for 6+ weeks (ciclopirox olamine 8% OR efinaconazole 10% OR amorolfine 5% weekly OR bifonazole/urea ointment daily)
 

Grade 3: Severe nail tip pain, symptomatic separation of the nail bed from the nail plate or nail loss, significantly limiting IADLs	Hold study drug (for up to 14 days), with weekly reassessments of clinical condition. When resolves to eligibility or baseline parameters, restart at a reduced dose ( Appendix IV ) below in consultation with the Study Chair.	Silver nitrate application weekly AND topical antibiotics AND vinegar soaks. a For signs of infection (periungal edema/erythema/ tenderness and/or discharge), obtain bacterial cultures, and then start the following: treatment with oral antibiotic for 2 weeks (cefadroxil 15 mg/kg/dose (up to 500 mg/dose) every 12 hours, ciprofloxacin 15 mg/kg/dose (up to 500 mg/dose) every 12 hours, or sulfamethoxazole/trimethoprim (TMP) 6 to 12 mg TMP/kg/day in divided doses every 12 hours;

		
maximum single dose: 160 mg TMP/dose).
 
For cases of severe/refractory infection consider intravenous antibiotics.
 
Consider dermatological and/or surgical evaluation.

Grade 4: life-threatening consequences, urgent intervention indicated	Discontinue study drug	Evaluation and therapy as clinically indicated

a Vinegar soaks consist of soaking fingers or toes in a solution of white vinegar in water 1:1 for 15 minutes every day. Examples of topical antibiotic ointments: Mupirocin 2%, gentamycin, bacitracin zinc/polymixin B
		

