**5.4 Definition of Dose-Limiting Toxicity (DLT)**

DLT will be defined as any of the following events that are possibly, probably or definitely attributable to protocol therapy. Dose limiting hematological and non-hematological toxicities are defined differently.

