5.4.1.2 Any Grade 1 visual disturbance that persists for  $\geq 4$  weeks

5.4.1.3 Any Grade 2 non-hematological toxicity that persists for  $\geq 7$  days and is considered sufficiently medically significant or sufficiently intolerable by patients that it requires treatment interruption.

Note: Allergic reactions that necessitate discontinuation of study drug will not be considered a dose-limiting toxicity.

5.4.1.4 Hyperphosphatemia will be reported as a DLT if a dose modification is required (as described in [Section 6.4](#) for serum phosphate of 7.0 or greater)

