**6.2 Dose Modifications for Non-Hematological Toxicity**

- 6.2.1 If a patient experiences non-hematological dose-limiting toxicity as defined in [Section 5.4.1](#), the treatment will be held. If the toxicity resolves to meet eligibility parameters or baseline within 14 days of drug discontinuation, the patient may resume treatment at a reduced dose as outlined in the dosing nomogram table in [Appendix IV](#). Doses reduced for toxicity will not be re-escalated, even if there is minimal or no toxicity with the reduced dose.
- 6.2.2 If a non-hematologic dose-limiting toxicity as defined in [Section 5.4.1](#) does not resolve to meet eligibility or baseline parameters within 14 days of drug discontinuation, the patient must be removed from protocol therapy. Any Grade 1 visual disturbance that persists for  $\geq 4$  weeks and does not resolve to meet eligibility or baseline parameters within  $\geq 4$  weeks of drug discontinuation must be removed from protocol therapy.
- 6.2.3 If non- hematologic dose-limiting toxicity recurs in a patient who has resumed treatment at the reduced dose, the patient must be removed from protocol therapy.

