**Guidelines for Management of Paronychia**

Grade and Definition	Study Drug Management	Medical Management
Grade 1: Nail fold edema or erythema; disruption of the cuticle	Continue study drug at current dose.	Topical antibiotics AND vinegar soaks a
Grade 2: Nail fold edema or erythema with pain; associated with discharge or nail plate separation; limiting instrumental ADL	
Continue study drug at current dose.
 
Consider study drug holding if no improvement in 1 to 2 weeks.
 
When resolves to ≤Grade 1 or baseline, restart at same or 1 dose level below in consultation with the Study Chair.
	
Topical antibiotics AND vinegar soaksa AND topical antifungal lacquer daily for 6+ weeks (ciclopirox olamine 8% OR efinaconazole 10% OR amorolfine 5% weekly OR bifonazole/urea ointment daily).
 
For signs of infection (periungal edema/erythema/tenderness and/or discharge), obtain bacterial cultures, and then start the following: treatment with oral antibiotic for 2 weeks (cefadroxil 15 mg/kg/dose (up to 500 mg/dose) every 12 hours, ciprofloxacin 15 mg/kg/dose (up to 500 mg/dose) every 12 hours, or sulfamethoxazole/trimethoprim (TMP) 6 to 12 mg TMP/kg/day in divided doses every 12 hours; maximum single dose: 160 mg TMP/dose).

Grade 3: Limiting self-care ADLs, surgical intervention, or intravenous antibiotics indicated	
Hold study drug (for up to 14 days), with weekly reassessments of clinical condition.
 
When resolves to eligibility or baseline parameters, restart at a reduced dose (Appendix IV) in consultation with the Study Chair.
	
Vinegar soaksa AND consider nail avulsion
 
For signs of infection (periungal edema/erythema/tenderness and/or discharge), obtain bacterial cultures, and then start the following: treatment with oral antibiotic for 2 weeks (cefadroxil 15 mg/kg/dose (up to 500 mg/dose) every 12 hours, ciprofloxacin 15 mg/kg/dose (up to 500 mg/dose) every 12 hours, or sulfamethoxazole/trimethoprim (TMP) 6 to 12 mg TMP/kg/day in divided doses every 12 hours; maximum single dose: 160 mg TMP/dose).
 
For cases of severe/refractory infection consider intravenous antibiotics.
 
Consider dermatological and/or surgical evaluation.

Grade 4: life-threatening consequences, urgent intervention indicated	Discontinue study drug.	Evaluation and therapy as clinically indicated

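### Grade 2 nail toxicity and paronychia: Section 6.7 permits a same-dose restart after a hold that can meet the Grade 2 DLT definition, for which Section 6.2 offers only a reduced dose

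*Combined protocol and SAP*

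**What the plan says.** Four parts of the protocol bear on a Grade 2 nail event or paronychia that leads to a hold.

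- **DLT definition (5.4 and 5.4.1.3).** A DLT must be "possibly, probably or definitely attributable to protocol therapy". The Grade 2 limb begins "Any Grade 2 non-hematological toxicity that persists for" at least 7 days, and adds that the event "is considered sufficiently medically significant or sufficiently intolerable by patients that it requires treatment interruption". The note beneath it gives one exception: "Allergic reactions that necessitate discontinuation of study drug will not be considered a dose-limiting toxicity". Nail events and paronychia are not excepted.
- **General dose rule (6.2.1 to 6.2.3).** For any non-hematological DLT, treatment is held. If the event resolves within 14 days off drug, "the patient may resume treatment at a reduced dose as outlined in the dosing nomogram table" in Appendix IV. Reduced doses are not raised again. A DLT that does not resolve in 14 days, or that recurs at the reduced dose, means removal from protocol therapy.
- **Skin disorders (6.6).** The dose is maintained for Grade 1 or 2. For intolerable Grade 2, drug is held and the dose is then reduced under 6.2.
- **Nail tables (6.7).** For Grade 2 nail toxicity: "Consider holding study drug if no improvement in 1 to 2 weeks". On recovery to Grade 1 or better, or to baseline: "restart at same or at a reduced dose". For Grade 2 paronychia the hold is worded almost identically, followed by "restart at same or 1 dose level below in consultation with the Study Chair". Neither row refers to 5.4.1.3 or 6.2.

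**The concern.** One and the same event can fall under two instructions. Read through 5.4.1.3 and 6.2, it is a DLT with a permanent dose reduction and a removal rule. Read through 6.7 alone, it is a hold after which full dose may resume, with nothing further said.

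At stake are the dose the patient returns to, whether a patient in the lowest BSA band stays on therapy, and whether the event is recorded as a DLT. Tolerability is a secondary aim (1.2.2) and Section 2.3.1 reports no earlier pediatric experience, so consistent DLT classification has value here. Section 5.3 asks for suspected DLTs to be reported to the Study Chair within 24 hours. An investigator working only from the 6.7 table would have no prompt to do so.

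**Working it through.** The plan gives no figure to reproduce. The check is a comparison of rules with simple arithmetic.

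**1. Can a 6.7 hold satisfy 5.4.1.3?**

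- Duration: 1 to 2 weeks is 1 × 7 = 7 to 2 × 7 = 14 days. The threshold is at least 7 days. An event that has stayed at Grade 2 for that time meets it.
- Interruption: the hold is an interruption. 5.4.1.3 also asks that the event be judged significant or intolerable enough to require it. 6.7 only says to consider a hold. This condition may or may not be met.
- Attribution: at least possible attribution is needed. This too may or may not be met.

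So a 6.7 hold can meet the definition, but does not do so automatically.

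**2. What each section then says**

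| | 6.2 (event is a DLT) | 6.6 (intolerable Grade 2 skin) | 6.7, Grade 2 rows |
|---|---|---|---|
| Dose on restart | Reduced only | Reduced, through 6.2 | Same or lower |
| Time limit | Removal if unresolved at 14 days | Through 6.2 | Not stated |
| Recurrence | Removal if at the reduced dose | Through 6.2 | Not stated |
| DLT status | DLT | Not stated, but refers to 6.2 | Not stated |

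The Grade 3 rows of both 6.7 tables limit the hold to 14 days and offer only a reduced dose, in line with 6.2. The gap is therefore in the Grade 2 rows. The agent table in 9.1.2 lists nail disorder under skin and subcutaneous tissue disorders, which brings 6.6 into play for nail events. It lists paronychia under infections, so 6.6 bears less directly there.

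**3. Is an exception implied by the drafting?**

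Elsewhere, a same-dose restart has a counterpart in the DLT section:

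- Grade 3 liver enzymes that recover within 7 days restart at the same dose (6.3.1), and 5.4.1.1 excludes them from DLT.
- Phosphate of 7.0-9.0 mg/dL restarts at the same dose (6.4), and 5.4.1.4 sets a specific DLT rule for hyperphosphatemia.

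Nail toxicity and paronychia have no such counterpart.

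**4. Size of the difference (Appendix IV)**

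Reduction = (assigned dose − reduced dose) / assigned dose.

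| BSA (m²) | Same dose (mg) | Reduced dose (mg) | Difference |
|---|---|---|---|
| 0.53-0.74 | 3 | Off protocol therapy | Continue or leave |
| 0.75-0.96 | 4 | 3 | 1/4 = 25% |
| 0.97-1.17 | 5 | 3 | 2/5 = 40% |
| 1.18-1.38 | 6 | 4 | 2/6 = 33% |
| 1.39-1.59 | 7 | 5 | 2/7 = 29% |
| ≥ 1.6 | 8 | 6 | 2/8 = 25% |

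**5. Effect on the analyses**

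The primary decision is at least 3 responses in 20 (11.3) and uses no DLT count. Section 11 contains no stopping rule based on DLTs. The toxicity tables in 11.4 are by type and worst grade, so labelling a Grade 2 nail event a DLT would not alter them.

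**The case against.** The strongest reply is that the sections can be read together. 6.7 makes the hold discretionary, whereas 5.4.1.3 needs an event that requires interruption, and 6.6 separates tolerable from intolerable Grade 2 events. On that reading, the choice in 6.7 between same and lower dose is coherent: same dose after a precautionary hold, lower dose when the event was intolerable and so a DLT.

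Much of this stands. A reader might infer that every Grade 2 hold under 6.7 is a DLT. The documents do not support that, because attribution and a judgement that interruption was required must both be present. What does not stand is that the text settles the matter. 6.7 does not link the choice of dose to that distinction, does not cross-refer to 5.4.1.3, 6.2 or 6.6, and leaves same-dose restart open for the events that do qualify.

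A second reply is central control. Both Grade 2 rows require consultation with the Study Chair on restart, Section 6.0 requires notice of any dosage modification, and under 14.4.2 the Study Chair enters DLT evaluations that the MATCH Chair, Vice Chair and Statistician review on a weekly call. A reader might infer that classification and dose would simply vary by site. These controls argue against that. They still give no criterion for deciding whether a given hold is a DLT, and they do not supply a same-dose option in 6.2.

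**Conclusion.** The inconsistency is in the current text but is confined to a subset: Grade 2 nail events or paronychia, held after 7 to 14 days without improvement, at least possibly attributable to therapy, and judged to require interruption. For these, the sections give different restart doses, different removal rules and an unclear DLT status. The dose difference is 25% to 40%. In the lowest BSA band it is 3 mg against leaving protocol therapy. This rests on reading 6.2.1 as excluding a same-dose restart, which is fair because it names no other resumption dose.

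A reader might infer from the agent table (nail disorder above 20%, paronychia at or below 20%, of 417 patients) that several of the 20 to 49 patients would be affected. The table does not support this. Its bands are not split by grade, duration or need for a hold, and no document gives the rate of the relevant subset, so the number is unknown.

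Nor should a reader infer a threat to the response result. The 3-in-20 rule is unaffected, and dose intensity is not a listed aim or analysis. The point concerns consistent patient management and DLT recording, and should be corrected on those grounds.

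**What to change.** Reconcile 5.4.1.3, 6.2, 6.6 and the Grade 2 rows of both 6.7 tables in one amendment:

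- State when a hold for Grade 2 nail toxicity or paronychia counts as a DLT, either by a cross-reference from 6.7 to 5.4.1.3 or by an explicit provision in the DLT section.
- Make the restart dose, the limit on the length of the hold and the consequence of recurrence agree across the sections.
- State whether 6.6 or 6.7 governs where a nail event falls under both.

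Which rule applies is for the clinical team to choose; this review does not favor one. The cost is amendment wording. Sample size, visit schedule and analysis do not change.

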**Guidelines for Management of Paronychia**

Grade and Definition	Study Drug Management	Medical Management
Grade 1: Nail fold edema or erythema; disruption of the cuticle	Continue study drug at current dose.	Topical antibiotics AND vinegar soaks a
Grade 2: Nail fold edema or erythema with pain; associated with discharge or nail plate separation; limiting instrumental ADL	
Continue study drug at current dose.
 
Consider study drug holding if no improvement in 1 to 2 weeks.
 
When resolves to ≤Grade 1 or baseline, restart at same or 1 dose level below in consultation with the Study Chair.
	
Topical antibiotics AND vinegar soaksa AND topical antifungal lacquer daily for 6+ weeks (ciclopirox olamine 8% OR efinaconazole 10% OR amorolfine 5% weekly OR bifonazole/urea ointment daily).
 
For signs of infection (periungal edema/erythema/tenderness and/or discharge), obtain bacterial cultures, and then start the following: treatment with oral antibiotic for 2 weeks (cefadroxil 15 mg/kg/dose (up to 500 mg/dose) every 12 hours, ciprofloxacin 15 mg/kg/dose (up to 500 mg/dose) every 12 hours, or sulfamethoxazole/trimethoprim (TMP) 6 to 12 mg TMP/kg/day in divided doses every 12 hours; maximum single dose: 160 mg TMP/dose).

Grade 3: Limiting self-care ADLs, surgical intervention, or intravenous antibiotics indicated	
Hold study drug (for up to 14 days), with weekly reassessments of clinical condition.
 
When resolves to eligibility or baseline parameters, restart at a reduced dose (Appendix IV) in consultation with the Study Chair.
	
Vinegar soaksa AND consider nail avulsion
 
For signs of infection (periungal edema/erythema/tenderness and/or discharge), obtain bacterial cultures, and then start the following: treatment with oral antibiotic for 2 weeks (cefadroxil 15 mg/kg/dose (up to 500 mg/dose) every 12 hours, ciprofloxacin 15 mg/kg/dose (up to 500 mg/dose) every 12 hours, or sulfamethoxazole/trimethoprim (TMP) 6 to 12 mg TMP/kg/day in divided doses every 12 hours; maximum single dose: 160 mg TMP/dose).
 
For cases of severe/refractory infection consider intravenous antibiotics.
 
Consider dermatological and/or surgical evaluation.

Grade 4: life-threatening consequences, urgent intervention indicated	Discontinue study drug.	Evaluation and therapy as clinically indicated

a Vinegar soaks consist of soaking fingers or toes in a solution of white vinegar in water 1:1 for 15 minutes every day. Examples of topical antibiotic ointments: Mupirocin 2%, gentamycin, bacitracin zinc/polymixin B
		

Dose Modifications for Visual Disturbances

Grade	Immediate Action	Subsequent Action
Grade 1	Hold erdafitinib until an ophthalmologic exam can be completed (if possible, within 7 days).	
 
• If the diagnosis is keratitis or retinal abnormality such as central serous retinopathy (CSR)/retinal pigment epithelial detachments (RPED) withhold erdafitinib until signs and symptoms have resolved. For retinal pathology perform OCT as appropriate and consider referral to a retinal specialist for further evaluation.
 
• Follow specific treatment as per the ophthalmologist's recommendation.
 
• If the toxicity resolves to < Grade 1 within 4 weeks according to ophthalmologic exam, resume erdafitinib therapy at the reduced dose (Appendix IV) level after consultation with the study chair per Section 6.2. Refer to Appendix IV for dose reduction information.
 
• Monitor for recurrence every 1-2 weeks for a month and as clinically appropriate thereafter.
 
• If there is no evidence of eye toxicity, resume erdafitinib therapy at the same dose level.
 

Grade 2	Hold erdafitinib until ophthalmologic exam is completed (if possible, within 7 days).	
 
• If the diagnosis is keratitis or retinal abnormality such as CSR/RPED, hold erdafitinib until signs and symptoms have resolved, stabilized. For retinal pathology perform OCT as appropriate and consider referral to a retinal specialist for further evaluation.
 
• Monitor for recurrence every 1-2 weeks for a month and as clinically appropriate thereafter.
 
• Follow specific treatment as per the ophthalmologist's recommendation.
 
• If there is no evidence of eye toxicity, resume erdafitinib therapy at the same dose level.
 
• If the Ophthalmology exam is normal and the toxicity resolves to < Grade 1 within 4 weeks or according to ophthalmologic exam, resume erdafitinib therapy at the reduced dose level (Appendix IV) after consultation with the study chair per Section 6.2.
 

Grade 3	Immediately stop erdafitinib and promptly refer subject to an ophthalmologist for evaluation with an ophthalmologic exam	
 
• Hold erdafitinib until eye exam is completed. If vision change is determined to be unrelated to erdafitinib, contact the study chair to discuss restarting of erdafitinib. Otherwise <math>\geq</math> Grade 3 visual disturbance will be considered a DLT and require a dose reduction as per Section 6.2 if resolves within 4 weeks.
 
• Follow specific treatment as per the ophthalmologist's recommendation.
 
• Monitor for recurrence every 1-2 weeks for a month and as clinically appropriate thereafter.
 
• If recurs, consider permanent discontinuation.
 

Grade 4	Permanently discontinue erdafitinib and promptly refer subject to an ophthalmologist for evaluation with an ophthalmologic exam	
 
• Refer to Section 13.0 for reporting guidelines; monitor resolution of eye finding until complete resolution, stabilization, or other off-study criteria are met (see Section 10.1)
 

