**5.4.1 Non-Hematological Dose-Limiting Toxicity**

- 5.4.1.1 Any Grade 3 or greater non-hematological toxicity attributable to the investigational drug with the specific exclusion of:
- Grade 3 nausea and vomiting of < 3 days duration
  - Grade 3 liver enzyme elevation, including ALT/AST/GGT that returns to

levels that meet initial eligibility criteria or baseline within 7 days. See [Section 6.3](#), and [Appendix XI](#) for values that represent thresholds between CTCAE grades.

Note: For the purposes of this study the ULN for ALT is defined as 45 U/L regardless of baseline.

- Grade 3 or 4 fever < 5 days duration.
- Grade 3 infection < 5 days duration.
- Grade 3 hypophosphatemia, hypokalemia, hypocalcemia or hypomagnesemia responsive to supplementation

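### For a drug-related Grade 3 visual DLT that recurs as a DLT at the reduced dose, Section 6.2.3 requires removal from protocol therapy, but the Grade 3 row of the visual table only says to consider stopping

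*Combined protocol and SAP*

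**What the plan says.** **DLT definition.** Section 5.4.1.1 counts as a DLT "Any Grade 3 or greater non-hematological toxicity attributable to the investigational drug with the specific exclusion of" a short list of events, none of them visual. Section 5.4.1.2 adds a further route, beginning "Any Grade 1 visual disturbance that persists for" and set at 4 weeks or more. Section 5.4.1.3 adds Grade 2 toxicity of at least 7 days that forces an interruption.

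**General rule.** Under Section 6.2.1, if a non-hematological DLT resolves "within 14 days of drug discontinuation, the patient may resume treatment at a reduced dose". Section 6.2.3 covers recurrence (the quotation starts just after the prefix *non-*): "hematologic dose-limiting toxicity recurs in a patient who has resumed treatment at the reduced dose, the patient must be removed" from protocol therapy.

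**Visual table, Grade 3 row.** Unless the vision change is judged unrelated to erdafitinib, the row says that "Grade 3 visual disturbance will be considered a DLT and require a dose reduction as per" Section 6.2 "if resolves within 4 weeks". Its last bullet is "If recurs, consider permanent discontinuation".

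**Visual table, other rows.** The Grade 1 and Grade 2 rows say "Monitor for recurrence every 1-2 weeks for a month and as clinically appropriate thereafter" but name no action if the event returns. The Grade 4 row requires permanent discontinuation.

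**The concern.** One identifiable patient falls under two instructions of different force. A drug-related Grade 3 visual event resolves, treatment restarts at the reduced dose, and a dose-limiting visual event returns. Section 6.2.3 takes the decision away from the investigator, while the last bullet of the Grade 3 row hands it back.

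A site could reasonably turn to the eye table first. The Patient Care Implications text in Section 9.1.1 sends eye-examination management to a dose-modification table, which it cites as Section 6.8. The Grade 3 row also already differs from Section 6.2.1 on timing, at 4 weeks against 14 days. A reader who treats the table as the more specific rule could rechallenge a patient whom 6.2.3 would remove, and two sites could handle the same event differently.

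The stake is vision in children. Section 2.3.1 reports no prior pediatric experience, and central serous retinopathy is the only adverse event of special interest in Section 13.3.1.

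**Working it through.** The plan states no figure on this point, so the check compares the texts and then counts who can be affected.

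**Step 1. Is the first event a DLT?** Yes. It meets 5.4.1.1, and the first bullet of the Grade 3 row says so as well.

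**Step 2. Can the patient resume at a reduced dose?** The row allows it after resolution within 4 weeks. Appendix IV gives the doses:

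| BSA (m²) | Start (mg) | Reduced (mg) | Second reduction |
|---|---|---|---|
| 0.53-0.74 | 3 | none: off protocol therapy | none |
| 0.75-0.96 | 4 | 3 | none |
| 0.97-1.17 | 5 | 3 | none |
| 1.18-1.38 | 6 | 4 | none |
| 1.39-1.59 | 7 | 5 | none |
| 1.6 and above | 8 | 6 | none |

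Bands where the situation can arise: 6 − 1 = 5 of 6. Bands with a second reduction: 0 of 6.

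**Step 3. What applies if the event recurs as a DLT at that dose?**

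| Source | Trigger | Instruction | Force |
|---|---|---|---|
| 6.2.3 | Non-hematological DLT recurs at the reduced dose | Remove from protocol therapy | Mandatory |
| Grade 3 row, last bullet | Recurrence, with no limit by grade, relatedness or dose | Consider stopping permanently | Discretionary |

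Both triggers are met.

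**Step 4. Does any section rank the two?** Sections 5.1, 5.2 and 10.1(b) point to Section 6 as a whole, which contains both. Section 9.1.1 points to the eye table but does not say that it overrides 6.2.3, and the table refers back to 6.2. The note on clinical judgment under the phosphate table is confined to phosphate. No order of precedence is stated.

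**Step 5. Which rows conflict with 6.2.3?**

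| Row | Instruction on recurrence | Conflict? |
|---|---|---|
| Grade 1 | None, so 6.2.3 alone applies | No |
| Grade 2 | None, so 6.2.3 alone applies | No |
| Grade 3 | Consider stopping | Yes, for a drug-related DLT at the reduced dose |
| Grade 4 | Permanent discontinuation at any occurrence | No |

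The inconsistency lies in 1 of 4 rows.

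**The case against.** The strongest reply is that the texts fit together and 6.2.3 governs.

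- The Grade 3 row sends the DLT to Section 6.2, and 6.2.3 is part of that section. Removing the patient complies with both texts.
- Section 6.2.2 contains a visual exception (4 weeks for a persistent Grade 1 disturbance), so the authors wrote eye carve-outs where they wanted them. The next clause, 6.2.3, has none. Where they wanted discretion over permanent discontinuation, in the phosphate table, they set conditions: clinical benefit and the Study Chair's agreement.
- The discretionary bullet has work of its own. It can cover a lower-grade recurrence that is not a DLT, or an event first judged unrelated and restarted after discussion with the chair. Section 6.2.3 reaches neither.
- The harm is partly blocked. A recurrent Grade 3 event re-enters the row, which requires an immediate stop and, if drug-related, a dose reduction that Appendix IV does not offer. Suspected or confirmed DLTs go to the Study Chair within 24 hours (5.3), the chair must be told of dose modifications (6.0), central serous retinopathy goes to CTEP-AERS even without hospitalization (13.3.1), and MATCH leadership reviews study data weekly (14.4.2).

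All of this stands, and it makes 6.2.3 the better reading. It does not remove the inconsistency. The row cites 6.2 for the dose reduction, and its recurrence bullet is not limited to events outside 6.2.3. The safeguards bring the case to the chair without saying which rule the chair should apply.

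**Conclusion.** This is a minor inconsistency in a patient-safety rule, worth correcting. It concerns a drug-related Grade 3 visual disturbance that recurs as a DLT after treatment resumes at the reduced dose, in patients with BSA of 0.75 m² or more. It is likely rare, but the documents give no recurrence rate, so no expected number can be stated.

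A reader might infer more than the documents support:

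- *That the conflict covers visual DLTs of every grade.* The competing wording appears only in the Grade 3 row. In the Grade 1 and 2 rows 6.2.3 stands alone, and silence there is not a contradiction.
- *That the protocol allows treatment to continue after a second dose-limiting eye event.* No text says that the eye table overrides 6.2.3, and the context favours 6.2.3.
- *That the 4-week against 14-day difference shows the table displacing Section 6.2.* It explains how a site might be misled, but it is a separate timing matter.
- *That the efficacy design is affected.* The A'Hern sample size of 20 and its decision rule do not depend on this wording.

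The conclusion assumes that the recurrence is drug-related and itself meets a DLT definition in 5.4.1. Outside those conditions, the discretionary bullet does not contradict 6.2.3.

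**What to change.** Replace the last bullet of the Grade 3 row with:

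> If a drug-related visual DLT recurs after resumption at the reduced dose, remove the patient from protocol therapy per Section 6.2.3; for other Grade 1-3 recurrences, consider permanent discontinuation in consultation with the Study Chair (Grade 4: permanently discontinue, as below).

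This aligns the row with 6.2.3, keeps discretion for recurrences that 6.2.3 does not reach, and leaves the Grade 4 stop intact. The Grade 1 and 2 rows need no change on this point.

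The change is one bullet in one table. Its cost is the loss of investigator discretion for the rare patient who is benefiting and has a second dose-limiting eye event. If the sponsor wants to keep that discretion, it should write the exception into 6.2.3 with stated conditions, as the phosphate table does.
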